3.1.4 Clinical studies

A first human dose trial (NN8640-3915) in healthy male adults (Japanese and non-asian subjects) investigated safety, tolerability (i.e. local tolerability reactions), PK and PD of s.c. doses of NNC0195-0092 (single and multiple dose) compared to placebo. Single doses were administered to non-asian subjects only, multiple doses were administered to both Japanese and non-asian subjects. NNC0195-0092 administered to healthy male subjects was well tolerated at all doses (single dose up to 0.32 mg/kg and multiple dose up to 0.24 mg/kg), with no serious safety issues or significant local tolerability issues identified. No differences in $AUC_{(0-\tau)}$ and C_{max} were observed between Japanese and non-Asian subjects. A significant dose-dependent IGF-I response was induced at all dose levels, with significantly increased IGF-I levels at all doses of NNC0195-0092.

In the trial NN8640-3947 multiple doses of NNC0195-0092 administered s.c. to AGHD patients were well tolerated at all doses investigated (0.02, 0.04, 0.08 and 0.12 mg/kg), with no serious safety issues or clinically significant local tolerability issues identified. The observed adverse events (AE) are overall similar to AEs seen in trials with daily hGH treatment. No anti NNC0195-0092 antibodies or anti hGH antibodies were detected.

The IGF-I response after once-weekly NNC0195-0092 (0.02 and 0.04 mg/kg) and once-daily Norditropin appear similar. The IGF-I profiles indicate that NNC0195-0092 may be suitable for once weekly dosing, with a clinical relevant dose range ≤ 0.08 mg/kg for AGHD.

3.1.5 Risks and benefits

The non-clinical safety programme of NNC0195-0092 reveals no special hazards for humans based on conventional studies of safety pharmacology, repeat-dose toxicity or genotoxicity. Non-clinical data is summarised in section [3.1.3](#).

Currently available data on clinical safety and efficacy of NNC0195-0092 is summarised in section [3.1.4](#). The safety profile of NNC0195-0092 has been evaluated in healthy adult subjects receiving single or multiple doses of the drug (NN8640-3915). Overall, the drug was well tolerated. All adverse events were mild, or moderate and primarily observed at the highest dose levels. Most common adverse events were: headache, peripheral oedema, joint pain, muscle pain, transient increase in blood sugar and insulin levels. In a recent trial in patients with adults with GHD (NN8640-3947) receiving multiple doses of the drug, the same safety profile of adverse events were registered. Overall, the safety profile of NNC0195-0092 observed so far is similar to the existing growth hormone products for daily administration e.g. Norditropin®.

Additional details on the trial product are described in the Investigator's Brochure (IB)¹⁷.

3.1.6 Norditropin® FlexPro®

Norditropin® is the registered trademark for Novo Nordisk's recombinant human GH product, somatropin. Norditropin® FlexPro® is the prefilled pen with liquid hGH to be used as comparator.

Norditropin® FlexPro® is currently approved in the EU countries for GHD, Turner syndrome, Short for Gestational Age (SGA), AGHD and growth retardation in prepubertal children due to chronic renal disease. In the US, Norditropin® FlexPro® is approved for GHD, Noonan syndrome, Turner syndrome, AGHD and SGA. In other parts of the world, the main therapeutic indications are GHD, Turner syndrome, growth retardation in prepubertal children due to chronic renal disease, SGA and AGHD. Norditropin® FlexPro® has in these subject populations proven to be a safe and efficacious treatment.

For further information please refer to the Summary of Product Characteristics (SmPC)¹⁸.

3.2 Rationale for the trial

The aim of the project is to develop a long-acting once-weekly GH product which is a safe and efficacious but has greater convenience and thus potentially better compliance compared to standard once daily GH treatment.

The aim of the trial is to investigate efficacy, safety and tolerability of multiple once weekly s.c. dosing of NNC0195-0092 in adults with GHD. This trial is a pivotal trial required for application for marketing authorisation for NNC0195-0092 in adults with GHD.

4 Objective(s) and endpoint(s)

4.1 Objective(s)

Primary objective

- To demonstrate the efficacy of once weekly dosing of NNC0195-0092 compared to placebo after 34 weeks of treatment in adults with growth hormone deficiency

Secondary objectives

- To evaluate the clinical safety of once weekly dosing of NNC0195-0092 during 34 weeks of treatment in adults with growth hormone deficiency
- To evaluate the efficacy and safety of NNC0195-0092 for up to 86 weeks of treatment in adults with growth hormone deficiency (i.e. during the main and extension periods of the trial)

4.2 Primary endpoint

- Change from baseline to end of main trial period (Week 34) in truncal fat percentage.

Body composition is measured by DXA; truncal fat percentage is defined as 100 times truncal fat mass (kg) divided by the sum of truncal fat mass (kg) and truncal lean body mass (kg)

4.3 Supportive secondary endpoints

*Key supportive secondary endpoint prospectively selected for posting on clinicaltrials.gov are marked below.

4.3.1 Supportive secondary efficacy endpoints

Changes from baseline to end of main trial period (Week 34) in the following variables will be used to address the primary objective:

- Truncal fat mass*
- Truncal lean body mass*
- Total fat mass
- Visceral adipose tissue (VAT)
- Android fat mass
- Gynoid fat mass
- Appendicular skeletal muscle mass (ASMM)
- Lean body mass

- IGF-I SDS
- IGFBP-3 SDS
- Scores of the following PRO questionnaires:
 - TRIM-AGHD (total and domain scores)
 - SF-36v2 (summary and domain scores)
- Lipid profile (total cholesterol, HDL- cholesterol, LDL-cholesterol and triglycerides)
- Cardiovascular parameters (hsCRP and IL-6)
- Body weight
- Waist circumference

Changes from baseline to end of extension period (Week 87) in all of the above mentioned variables as well as bone mineral content (BMC) and bone mineral density (BMD) will be used to support the secondary objective regarding evaluation of efficacy during the extension period.

- Compliance with treatment will be evaluated based on time stamps from the electronic pen caps (ecaps) in the extension period and based on diary data in the main trial and the extension period. The endpoint is defined as percentage of doses taken as prescribed.
- Scores of PRO questionnaire TSQM (domain scores) will be evaluated at weeks 34 and 87

Visceral adipose tissue and android and gynoid fat mass will be assessed only if the DXA scanner permits.

4.3.2 Supportive secondary safety endpoints

The following endpoints will be used to support the secondary objectives of evaluation of safety in both the main (up to week 35) and extension (up to week 88) trial periods:

- Incidence of adverse events, including injection site reactions*
- Occurrence of anti-NNC0195-0092 antibodies*
- Incidence of technical complaints
- Changes from baseline in physical examination, ECG results and vital signs
- Changes from baseline in clinical laboratory test results including haematology, biochemistry, fasting glucose, fasting insulin, steady state beta cell function (%B) and insulin resistance (IR) (HOMA estimates), and HbA1c levels

5 Trial design

5.1 Type of trial

This is a multicentre, multinational, randomised, parallel-group, placebo-controlled (double blind) and active-controlled (open) trial to compare the efficacy and safety of once weekly dosing of NNC0195-0092 with once weekly dosing of placebo and daily dosing of Norditropin® FlexPro® in adults with GHD during a 35-week period, with a 53-week extension period.

[figure not shown]

Figure 5-1 Trial design

Two hundred and eighty (280) subjects will be randomised in a 2:2:1 ratio to receive NNC0195-0092, Norditropin® FlexPro® or placebo during a 35-week period (8 weeks of titration, followed by 26 weeks of treatment and 1 week of washout). The randomisation will be stratified according to two region levels (Japan and all other countries), sex (male and female) and diabetic status (diagnosed with diabetes mellitus vs. not diagnosed with diabetes mellitus). All subjects completing the 35-week period will continue their active treatment with NNC0195-0092 weekly injection or Norditropin® FlexPro® daily injection in a non-placebo-controlled design for an additional 53-week extension period (8 weeks of titration, followed by 44 weeks of treatment and 1 week of washout). Placebo subjects will be switched to NNC0195-0092 treatment and Norditropin® FlexPro® subjects will be re-randomised 1:1 to NNC0195-0092 or Norditropin® FlexPro® within the same strata as used for the first randomisation. During the extension period subjects will be seen on a regular basis for adverse events, safety laboratory measurements, and efficacy.

The trial flow is depicted in [Table 2-1](#) (main trial period) and [Table 2-2](#) (extension period).

A blinded interim reporting of all safety parameters as described in sections [8.5](#) and [17.5](#) is planned to be done when 50 subjects randomised to NNC0195-0092 have completed the main trial. Data for

all subjects up to week 35 (see [Table 2-1](#)) who have completed the main trial at this time will be included.

5.2 Rationale for trial design

The randomised, placebo-controlled, partly double-blind, active controlled, multicentre design is based on regulatory scientific advices. The inclusion of the active controlled arm in an open design is to compare efficacy and safety including local tolerability of NNC0195-0092 to daily Norditropin[®] FlexPro[®] treatment. A multinational approach has been chosen to address that the results are applicable for subjects with different demographic characteristics. The parallel design has been chosen instead of a cross-over design as a cross-over trial would not be possible due to carry-over effects on e.g. body composition. The titration period allows for four opportunities to adjust the dose of NNC0195-0092 to achieve an optimal targeted serum IGF-I concentration. The 26-week fixed dose treatment period is the expected minimal time needed for changes of body composition to develop. The washout periods are included to confirm the antibody response.

The extension period is an outcome of HA interactions and allows for longer-term evaluation of efficacy and safety of NNC0195-0092. Subjects treated with Norditropin[®] FlexPro[®] during the main trial are re-randomised to NNC0195-0092 and Norditropin[®] FlexPro[®] at the beginning of the extension to obtain additional safety data for once weekly treatment and still compare efficacy and safety between the active treatments.

5.3 Treatment of subjects

Subjects will be randomised in a 2:2:1 ratio to receive either NNC0195-0092 (approximately 112 subjects), Norditropin[®] FlexPro[®] (approximately 112 subjects, open label towards both other arms) or placebo (approximately 56 subjects, double blind towards NNC0195-0092).

Time of injections:

- NNC0195-0092 and placebo subjects will inject themselves once a week s.c. in the morning no later than 10 AM to ensure consistency of PK/PD with previous trials. On site visit days this can be extended until 12:00 PM (noon). Trial drug must not be administered in the morning before relevant visit procedures have been performed (see section [2](#)).
- Norditropin[®] FlexPro[®] subjects will inject themselves daily s.c. in the evening (to reflect standard treatment practice) throughout the trial and only in the morning (no later than 12 PM and at least 12 hours after injection the evening before) during observed trial drug administration. Injections with Norditropin[®] FlexPro[®] the night before blood sampling for anti-hGH antibodies must occur at least 12 hours prior to sampling.

For the first 35-week treatment period, the first dose will be administered by the subject on Day 0 (randomisation), and the last dose will be administered by the subject at home during Week 33. For the extension period, the first dose will be administered in the beginning of Week 35, and the last

dose will be administered by the subject at home during Week 86. No drug will be administered at the Week 34 and Week 87. The maximal treatment duration for a single subject is 86 weeks.

Subjects in all three arms will be trained in the use of the pen-injector and inject themselves under the supervision of the site staff at the visit and will inject themselves at home (see sections [2](#) and [8.7](#)).

Weight loss medications known to affect body weight substantially are not allowed during the trial.

5.3.1 Dose titration

During the first 8 weeks the dose will be titrated every second week starting from Week 2. The last dose adjustment in the main trial period will be done at Week 8. This allows four opportunities for dose adjustment (Week 2, 4, 6, and 8). Dose titration is based on blinded insulin like growth factor-I standard deviation score (IGF-I SDS) values which will be uploaded from the central laboratory to the interactive voice/web response system (IV/WRS) which calculates the next dose. Subjects will come to the clinic 1 week and 3 days after the previous dose adjustment visit for an IGF-I, IGFBP-3 and PK blood sample draw. Handling deviations from this schedule is described in section [5.3.5](#). Dose adjustments are performed at Week 0 (starting dose) 2, 4, 6, and 8, i.e. four days after the IGF-I titration samples have been collected. The blood draw 1 week and 3 days after the dose adjustment visit at week 8 is to record the IGF-I level attained following the last dose adjustment at Week 8. Dose adjustment at Week 6 will be instructed over the phone. After last dose adjustment (if any) at Week 8, the individual dose level is fixed.

Besides the IGF-I based dose adjustment during the titration period, dose reduction can be considered during the entire study period (including the two titration periods) at the investigator's discretion for safety concerns. If adverse events with an probable relationship to the trial drug are persistent but continuation in the trial is acceptable as judged by the investigator and subject, dose reduction in steps of 25% can be considered. The procedure for dose reduction is described in section [6.5](#).

If a subject reports symptoms of GH related AEs at a dose adjustment visit, the dose adjustment call in the IV/WRS must be performed prior to potentially reducing the dose by 25% as the IGF-I based titration might reduce the dose.

5.3.2 Dose titration algorithm

The titration algorithm depends on the obtained difference in IGF-I SDS between the value at any time during the titration period and the IGF-I SDS value at randomisation. In order to accommodate subjects requiring a high dose, the increments can be higher if only a small change from randomisation has been observed (see [Table 5-2](#) and [Table 5-4](#)).

The size of the dose adjustments in [Table 5–2](#) was derived based on PK/PD analysis of data from previous trials with NNC0195-0092. The dose titration of Norditropin® FlexPro® ([Table 5–4](#)) is designed based on clinical experience, interim results from NN8640-3947 which contained a comparator arm with daily Norditropin® FlexPro® doses and also in alignment with a titration algorithm from literature¹².

5.3.3 Titration for subjects treated with either NNC0195-0092 or Placebo

The starting doses of NNC0195-0092 at Visit 2 (Day 0) are described in table [Table 5–1](#), dose titration in [Table 5–2](#). The starting doses were tested to be safe in NN8640-3947 and are expected to be below the ideal maintenance dose for IGF-I SDS target for most subjects.

Table 5–1 Starting doses for NNC0195-0092 or placebo subjects

Group	Starting dose of NNC0195-0092*	Starting dose converted to daily exposure
Subjects between 23 and 60 years of age	1.5 mg/week	0.214 mg/day
Females on oral oestrogen irrespective of age	2.0 mg/week	0.286 mg/day
Subjects older than 60 years	1.0 mg/week	0.143 mg/day

*The starting doses are expected to be below the ideal maintenance dose for IGF-I SDS target for most subjects. Individual adjustment of dose based on individual IGF-I response will be performed during the first 8 weeks.

Table 5–2 Dose Titration Algorithm for NNC0195-0092 or placebo subjects

IGF-I SDS Interval (1 week and 3 days after last dose adjustment)	Increment/reduction of weekly dose	
	Change IGF-I SDS from screening > 1	Change IGF-I SDS from screening ≤ 1
IGF-I SDS > 3	-1 mg	
1.75 < IGF-I SDS ≤ 3	-0.5 mg	
-0.5 < IGF-I SDS ≤ 1.75	-	+0.5 mg
-2 < IGF-I SDS ≤ -0.5	+0.5 mg	+0.5 mg
IGF-I SDS ≤ -2	+1 mg	+1.5 mg

The minimum weekly dose of NNC0195-0092 is 0.1 mg. If the algorithm returns a dose of less than 0.1mg, the weekly dose of NNC0195-0092 must be 0.1 mg. The maximum weekly dose of NNC0195-0092 is 8 mg.

If NNC0195-0092 or placebo subjects forget or are unable to inject the dose in the morning, they have to take the drug as soon as possible during the same day. If the subjects have failed to inject the trial product on the planned dosing day, they should contact the trial site since the blood

sampling and subsequent visit will potentially have to be rescheduled (see section 5.3.5). Injections must remain in the body areas of thighs and/or abdomen with rotation within these body areas.

Titration of placebo subjects will mirror titration of NNC0195-0092 subjects to avoid un-blinding. Subjects in the placebo group will also receive instructions on dose adjustment to mimic the pattern of dose adjustment in subjects receiving NNC0195-0092 treatment.

5.3.4 Titration for subjects treated with daily Norditropin® FlexPro®

The starting doses of Norditropin® FlexPro® given daily from Visit 2 (Day 0) is described in [Table 5-3](#), dose titration in [Table 5-4](#).

Table 5-3 Starting doses for Norditropin® FlexPro® subjects

Group	Starting dose of Norditropin® FlexPro®*
Subjects between 23 and 60 years of age	0.2 mg/day
Females on oral oestrogen irrespective of age	0.3 mg/day
Subjects older than 60 years	0.1 mg/day

*The starting doses are expected to be below the ideal maintenance dose for IGF-I SDS target for most subjects. Individual adjustment of dose based on individual IGF-I response will be performed during the first 8 weeks.

Table 5-4 Dose Titration Algorithm for Norditropin® FlexPro® subjects

IGF-I SDS Interval (1 week and 3 days after last dose adjustment)	Increment/reduction of daily dose	
	Change IGF-I SDS from screening > 1	Change IGF-I SDS from screening ≤ 1
IGF-I SDS > 3	-0.1 mg/day	
1.75 < IGF-I SDS ≤ 3	-0.05 mg/day	
-0.5 < IGF-I SDS ≤ 1.75	-	+0.05 mg/day
-2 < IGF-I SDS ≤ -0.5	+0.05 mg/day	+0.05 mg/day
IGF-I SDS ≤ -2	+0.1 mg/day	+0.2 mg/day

The minimum daily dose of Norditropin® FlexPro® is 0.05 mg. If the algorithm returns a dose of less than 0.05mg, the weekly dose of Norditropin® FlexPro® must be 0.05 mg. The maximum daily dose of Norditropin® FlexPro® is 1.1mg.

If Norditropin® FlexPro® subjects forget or are unable to give the dose in the evening they should skip the dose and continue on the next evening with the next scheduled dose. If a subject failed to inject the trial product the evening before a planned IGF visit, the subject should contact the trial site since the IGF visit and subsequent visits will have to be rescheduled, i.e. postponed two weeks.

5.3.5 Deviations from titration schedule

The dose titration schedule in the protocol must be followed in order to allow titration to an optimal therapeutic dose for all subjects. Four dose adjustment evaluations are required for optimal dose titration.

If for any reason a subject cannot be dose titrated on a scheduled dose adjustment day (e.g.: IGF-I value not available, subject comes for IGF-I sampling in a non-fasting state),

- the **previous IGF-I sampling visit** will, depending on whether the visit has taken place or not,
 - be repeated two weeks later as an unscheduled if the visit has already taken place
 - **or** be rescheduled to two weeks later if it has not taken place
- the **affected dose adjustment visit** will be rescheduled to two weeks later
- all **subsequent visits** during the titration periods will be rescheduled to two weeks later
- the **fixed dose IGF-I sample visits** (i.e. V11 and V24, respectively) will be rescheduled to two weeks later.

Subsequent trial visits after V11 and 24 respectively will not be postponed.

As an exception visits may be rescheduled up to two times during each titration period (allowing for a maximum of 6 opportunities for dose adjustment evaluation). If a subject has not completed at least 3 dose adjustment evaluations, this will be considered a PD as fewer than three completed dose adjustment evaluations are not expected to be sufficient to achieve therapeutic doses in a majority of subjects.

Deviations from the IV/WRS based dose titration other than those described above and dose reduction in steps of 25% will not be considered protocol deviations, however the reason for deviating must be recorded. Based on this information it may be decided to ask for additional information regarding the deviation (see section [14.1](#)). If the answer explains the deviation no further action will be taken.

5.3.6 Treatment during the extension period

After the main trial period NNC0195-0092 subjects will continue once weekly treatment. Placebo subjects will be switched to NNC0195-0092 treatment and Norditropin[®] FlexPro[®] subjects will be randomised 1:1 to NNC0195-0092 or Norditropin[®] FlexPro[®]. The extension period consist of treatment for 52 weeks (followed by 1 week washout). Dose titration will be repeated for all subjects during the first 8 weeks of the extension period as described for the main trial period. All subjects will start on the starting doses as described in section [5.3.3](#).

The extension period is considered as open label but blinding between NNC0195-0092 and Placebo during the 35-week main trial will be maintained throughout the trial. After database lock of the extension period the trial sites will be informed about the subject's treatment allocation during the 35-week treatment period.

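### Section 5.3.6 starts every extension subject on the doses of section 5.3.3 and does not cite section 5.3.4, the only source of Norditropin starting doses

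*Protocol*

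**What the plan says.** Protocol section 5.3.6 describes who receives what in the extension. NNC0195-0092 subjects continue, placebo subjects switch to NNC0195-0092, and Norditropin "subjects will be randomised 1:1 to NNC0195-0092 or Norditropin". Two sentences then govern dosing. The first is "Dose titration will be repeated for all subjects during the first 8 weeks of the extension period as described for the main trial period". The second is "All subjects will start on the starting doses as described in section" 5.3.3. It makes no exception for any group and cites no other section.

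The heading of the cited section is "5.3.3 Titration for subjects treated with either NNC0195-0092 or Placebo", and its starting-dose table is titled "Starting doses for NNC0195-0092 or placebo subjects". The doses are weekly, with a second column converting them to mg/day.

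Norditropin has its own section, 5.3.4: "The starting doses of Norditropin® FlexPro® given daily from Visit 2 (Day 0) is described in" Table 5–3. Those doses are daily. No other table in the protocol gives Norditropin starting doses.

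**The concern.** Read literally, a subject allocated at Week 35 to daily Norditropin is sent to the starting-dose table of a different product in a different unit. This is an operative dosing instruction, so it should give one clear answer for every subject it covers.

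The affected group also matters to the extension. Section 5.2 says that Norditropin subjects are re-randomised partly so that the active treatments can still be compared. Section 17.4.1.1 plans an exploratory Week 87 comparison of the group on NNC0195-0092 throughout with the group on Norditropin throughout. If sites, or whoever specified the IV/WRS, resolved the instruction differently, restart doses in the comparator could be inconsistent. Adverse events and dose paths early in the second titration would then be harder to interpret.

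**Working it through.** **1. Which subjects are covered correctly.** Subjects continuing on NNC0195-0092, subjects switched from placebo, and Norditropin subjects re-randomised to NNC0195-0092 all receive NNC0195-0092 in the extension, so 5.3.3 fits them. Only those re-randomised to Norditropin are misdirected.

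**2. How many.** Section 5.3 plans about 112 subjects in the Norditropin arm. Section 17.1 assumes 104 per active arm complete the main period. With 1:1 re-randomisation:
- 112 / 2 = 56 (no loss)
- 104 / 2 = 52 (planned completers)

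**3. Reproducing the protocol's own conversion.** Table 5–1 gives 1.5, 2.0 and 1.0 mg/week. Dividing by 7:
- 1.5 / 7 = 0.214 mg/day
- 2.0 / 7 = 0.286 mg/day
- 1.0 / 7 = 0.143 mg/day

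All three agree with the table's conversion column.

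**4. Comparing the two tables.** Difference = Table 5–1 converted minus Table 5–3; ratio = Table 5–1 converted / Table 5–3.

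| Group | Table 5–1, mg/day | Table 5–3, mg/day | Difference | Ratio |
|---|---|---|---|---|
| 23 to 60 years | 0.214 | 0.2 | +0.014 | 1.07 |
| Females on oral oestrogen | 0.286 | 0.3 | −0.014 | 0.95 |
| Over 60 years | 0.143 | 0.1 | +0.043 | 1.43 |

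The tables are therefore not interchangeable even in a common unit. The smallest non-zero step in Table 5–4 is 0.05 mg/day, and all three differences are smaller than that. The conversion is simple arithmetic on milligrams and says nothing about whether the two products are equivalent per milligram.

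**5. Whether an amendment corrects it.** The amendment to version 2.0 dated 04 Jul 2014 works through sections 5.3.2 to 5.3.6. Its entry for 5.3.6 (2.1.13) changes only the length of the main treatment period. The Japan-only amendment changes the maximum Norditropin dose in 5.3.4. Amendment 6 touches 5.3.1 and 5.3.5. None of these entries alters the cross-reference. The SAP rests on protocol version 6.0, whose full text is not supplied, so a correction made there without an entry cannot be excluded.

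**The case against.** The strongest reply is that nobody would be misled. The preceding sentence of 5.3.6 repeats the main-period titration for all subjects, and for Norditropin that description is 5.3.4. Table 5–1 is labelled by product and unit, Table 5–3 is the only table labelled for Norditropin, and section 10 ties the IV/WRS to the algorithm in section 5.3 as a whole. This largely stands as evidence that the reference is incomplete rather than a deliberate change of dose. It does not remove the defect: the preceding sentence concerns titration, while the next one specifically governs the starting dose and names only 5.3.3.

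Three stronger readings are tempting, and the documents do not support them.

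- **A several-fold dosing error.** If the mg/week figures were entered as mg/day, they would be 1.5 / 0.2 = 7.5, 2.0 / 0.3 = 6.7 and 1.0 / 0.1 = 10 times Table 5–3. That requires ignoring the product label, the unit and the adjacent daily column. Two of the three values would also exceed the 1.1 mg daily maximum in 5.3.4.
- **Section 5.3.4 cannot apply in the extension because it is worded for Visit 2.** Section 5.3.3 is worded for Visit 2 (Day 0) in the same way, so this does not separate the two.
- **A distorted Week 87 comparison.** Four IGF-I-based adjustments and 44 fixed-dose weeks follow the restart. Section 17.5 says the extension contributes no confirmatory results, and section 17.4.1.1 treats its efficacy models as exploratory. A lasting effect is not shown.

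**Conclusion.** The point holds as an internal inconsistency in a dosing instruction: 5.3.6 conflicts with 5.3.4, and with its own preceding sentence, for subjects allocated to Norditropin in the extension. It concerns about 52 to 56 subjects, assuming the planned arm size, the planned completion rate and an even split.

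On the daily-exposure reading, the tables differ by 0.014 to 0.043 mg/day in absolute terms. The 43% relative difference in subjects over 60 looks large because the Table 5–3 dose is small; in absolute terms it is less than one titration step. The primary endpoint is measured at Week 34, before the extension begins, so it is unaffected, as are the sample size, power and alpha.

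A reader might infer that the Norditropin arm was in fact restarted on the wrong doses. The documents do not show that. They show only that the text, followed literally, points to the wrong product's table. The conclusion rests on version 2.0 and the supplied amendment entries.

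**What to change.** The sponsor should reconcile 5.3.6 with 5.3.3 and 5.3.4, so that the source of the starting dose at Week 35 is stated separately for subjects allocated to NNC0195-0092 and for subjects allocated to Norditropin. The text of version 6.0 should be checked first, in case this has already been done. The IV/WRS extension specification should then be compared with the reconciled text. Which dose or rule applies is for the sponsor to settle, and none is proposed here.

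The cost is a sentence or two in the protocol and one specification check. No analysis, sample size or SAP text needs to change.
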